5.2 Prior and Concomitant Therapy

Participants will be allowed to take their usual outpatient medications. In order to facilitate this, participants will bring these medications with them to the CHPS on the day of admission and they will be administered under the supervision of the nursing staff during the course of their in-patient stay. Participants will be allowed to take acetaminophen as needed for minor ailments, such as a headache. Consumption of concomitant medications will be recorded in the study records daily. Participants will not be permitted to take any medications listed in the exclusion criteria during their participation in the study, prior to discharge from CHPS.

5.3 Supervision of access to food outside of the study protocol

In order to prevent access to food outside of the study protocol, participants will be accompanied by a member of the research staff whenever they leave the CHPS. When sufficient staff is available to supervise the participant, participants will be allowed to walk outside.

5.4 Activity Level

Once a participant is determined to be eligible, they will be given a Fitbit Flex. Participants will be required to wear this Fitbit Flex for at least 3 days prior to admission to CHPS to record the number of steps they take daily. The study team will calculate the average number of daily steps the participant took during the 3 days prior to admission. During the inpatient stay, participants will be required to attain within 10% of the average number of daily steps that they took in the 3 days prior to admission. To achieve this, participants will be escorted on walks outside of the inpatient unit by a coordinator, as needed.

6 Study Procedures

The sequence of study procedures is summarized in Section 6.2. The study procedures section is divided into two parts, one describing the collection methods of samples for metabolic and microbial profiling and a second describing the sequence of events.

6.1 Sample collection methods for metabolic and microbial profiling

6.1.1 Urine sample collection and storage

There is increasing evidence that the composition of the gut microbiome influences the metabolic profile of blood, urine, and other tissues.³⁰⁻³² Urine will be collected at the post-screening visit and during the inpatient stay. During the post-screening visit, urine will be collected following an overnight fast. During the inpatient stay, urine samples will be collected daily prior to 09:00h after an overnight fast. Up to 15 mL of urine will be obtained for each sample, aliquoted into three 5ml aliquots, and frozen at minus 80°C for use in metabolomic studies.

6.1.2 Blood sample collection and storage

Blood will be collected after an overnight fast prior to breakfast at the screening visit, at the post-screening visit, and on Days 1-4, 8, 10, and 11 of the inpatient study. Approximately 16cc of blood will be collected for metabolomics at each collection. Plasma will be separated from the blood samples. The plasma will be stored frozen at minus 80°C for use in metabolomic studies. Peripheral blood monocytes (PBMCs) will also be collected from the same samples and stored at minus 80°C for potential future use in cell phenotyping studies.

Participants may be contacted and asked to return 1 month after discharge for a follow-up blood collection.

6.1.3 Stool sample collection

Stool will be collected from the inpatient participants daily. Only the first sample of each day will be aliquoted and frozen. Subsequent samples (if available) will be weighed and the weight will be recorded. Each stool specimen that is collected will be processed in the same manner. The participant will be provided with a collection device to be placed in the commode that allows for separation of urine and feces, and keeps the feces separated from the toilet water. After they have finished voiding their first stool of the day, the specimen will be immediately processed according to the following protocol by the CHPS nurses. Using vials with small spoons attached to the lid, a small amount of stool will be scooped on to the spoon from the surface of the stool sample and leveled off with a tongue depressor. The weight of the sample will be recorded. A minimum of seven samples will be obtained from one stool collection. All samples will be labeled with the subject ID #, and the date of collection from the volunteer. The core sample will be labeled the same way. The aliquoted samples and the core sample will be immediately frozen at minus 80°C. The nurses will rate the sample based on the Bristol Stool Chart. Residual stool samples will be stored into up to five 15ml coring vials. Subsequent stools will be weighed in the collection device, rated on the Bristol Stool Chart, and then discarded.

In order to have a baseline stool sample prior to study diet, participants will be required to collect a stool sample prior to the post-screening visit. Participants will also collect a stool sample on the day prior to admission to CHPS. Study staff will provide the participant with collection materials and instructions for collecting the stool at home and bringing it in to study staff. Immediately after voiding the sample, the participant will put a small amount of stool into a spoon-top vial containing ethanol. They will label this vial and the collection device containing the remainder of the stool sample with the date of collection, and will rate the stool on the Bristol Stool Chart. They will then arrange a drop-off time with the study coordinator within 48 hours of sample collection. The study coordinator will bring this stool sample to the study lab on the 9th floor Biomedical Research Building (BRB). Lab personnel will aliquot the stool sample into a minimum of 7 spoon-top vials.

Participants may be asked to provide a stool sample 1 month after discharge. In addition, follow-up stool samples (which may be collected every 3 months for up to 5 years after the participant's last study day) may be collected and will be processed in the same manner as the inpatient samples. The collection kit may be shipped to the participant's home and the participant will either return the stool sample to study staff or ship it to [name] lab at the University of Pennsylvania.

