6.2.4.6 Sample collection

Blood, urine, and feces samples will be obtained. Up to 15 ml of urine samples will be collected prior to 09:00h after an overnight fast starting at midnight. Approximately 16cc of blood will be collected for metabolomics at each collection following an overnight fast prior to breakfast. Participants will be provided a stool collection kit to collect a stool sample on the day prior to admission or on the morning of admission. The first stool sample will be weighed, aliquoted and frozen. Participants will collect stool from all subsequent bowel movements. This stool will be weighed, the weight recorded and discarded. In addition, a stool sample will be collected by the participant at home either the day prior to Visit 3 or the morning of Visit 3. Participants will bring the stool sample to the visit. Study staff will provide the participant with collection materials and instructions for collecting the stool at home and returning it to study staff (See section 6.1.3).

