7.2.1 Determining the effect of CMC on fecal and mucosal microbiome composition

We will first compare the bacteria taxa in each fecal stool communities sampled at baseline, after the 3 day emulsifier free period and during the intervention period (total of 96 stool samples and 16 biopsy samples per treatment arm – 8 participants on each diet) to determine within-diet and between-diet variation prior to the administration of antibiotics. The analyses will be conducted separately for microbiomes in fecal samples and also in colonic mucosa samples. We will employ both of our methods (PCoA and proportion of the community represented by different taxa) to summarize the data at each time point. Besides comparing the microbiome among the treatment groups at day 11, we will also perform repeated measurement analysis of variance (RM-ANOVA) to study the time effects on microbiome and potential time and diet interaction effects for our data on fecal samples. The outcomes of such RM-ANOVA are the significant principal components summarizing the bacterial taxa.

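### Home-collected baseline stools are handled differently from inpatient stools, so the home-versus-inpatient part of the time effect and within-arm fecal changes are confounded with handling

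*Combined protocol and SAP*

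**What the plan says.** Section 6.1.3 describes inpatient handling first: "the specimen will be immediately processed according to the following protocol by the CHPS nurses", and then "The aliquoted samples and the core sample will be immediately frozen at minus 80°C".

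The same section gives a different route for stools collected at home: "Immediately after voiding the sample, the participant will put a small amount of stool into a spoon-top vial containing ethanol". The rest stays in the collection device. On delivery, "They will then arrange a drop-off time with the study coordinator within 48 hours of sample collection". After that, "Lab personnel will aliquot the stool sample into a minimum of 7 spoon-top vials". No storage temperature or time of freezing is given for the remainder, and the plan does not say whether the ethanol portion or the remainder goes to each assay.

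Sections 6.2.3.2 and 6.2.4.6 have the home stool passed on the day before the visit or that morning, and brought to the visit. For Day 1, Section 6.2.4.6 also states: "The first stool sample will be weighed, aliquoted and frozen". It does not make clear whether that is the home stool or one passed on the unit. Section 5 starts CMC at dinner on Day 1.

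Section 7.2.1 compares stools from baseline, the end of the emulsifier-free period and the intervention, 96 per arm, and uses RM-ANOVA "to study the time effects on microbiome and potential time and diet interaction effects". Section 7.2.3 allows unpaired between-group or paired within-group t-tests for data that include fecal lipocalin-2. Section 6.4.3 sends each fecal sample to sequencing, meta-transcriptomics and bioactive LPS and flagellin assays.

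**The concern.** The Visit 2 baseline is a home sample, and the post-washout reference probably is too. The intervention stools are inpatient samples. A move from the first group to the second is a change of study period and also a change of preservation: ethanol, or delayed freezing, against immediate freezing. If handling shifts a fecal measure, that shift appears in the time main effect and in any before/after comparison within an arm. The plan has no sensitivity analysis or restriction that would show it.

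At stake is a handling artefact being reported as a response to the controlled diet, or, within the CMC arm alone, as a response to CMC. Paired within-group analyses are a stated part of the plan: Section 7.1 gives 80% power for a paired difference of 1.15 SD.

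**Working it through.** **1. Reproduce the plan's count.** Section 7.2.1 gives 96 stools and 16 biopsies per arm, with 8 participants per arm.

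- 96 / 8 = 12 stools per participant; 16 / 8 = 2 biopsy days (Days 1 and 11).
- Reading A: 2 home stools + inpatient Days 2–11 = 2 + 10 = 12; 12 × 8 = 96.
- Reading B: Visit 2 home stool + Days 1–11 on the unit (one way to read the schedule table in Section 6.2) = 1 + 11 = 12; 12 × 8 = 96.
- Two home stools + inpatient Days 1–11 = 13; 13 × 8 = 104, which does not match.

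**2. Home-handled share.** Reading A: 2 × 8 = 16 of 96 per arm (16.7%). Reading B: 1 × 8 = 8 of 96 (8.3%). The documents do not decide between them.

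**3. Length of the wait.** The ceiling in Section 6.1.3 is 48 h. Collection on the day before or the morning of the visit implies less. On assumed clock times (passed at 00:00 the day before, handed over at 08:00), the longest wait is 24 + 8 = 32 h. A stool passed on the morning of the visit waits far less. The ethanol portion does not wait unpreserved, but it differs from the inpatient samples in preservative.

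**4. Which tests are exposed.** No handling effect is given, so the shift h is varied. Assumptions: true time and diet effects zero, total SD 1, within-person correlation ρ = 0.5, h added to home stools only, two-sided 5% tests. With k home stools out of 12, d is the inpatient mean minus the home mean, and

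SD(d) = √[(1 − ρ)(1/(12 − k) + 1/k)].

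- k = 2: √[0.5 × (0.1 + 0.5)] = 0.548
- k = 1: √[0.5 × (0.0909 + 1)] = 0.739

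The t statistic for n participants has noncentrality h√n / SD(d), with n − 1 degrees of freedom. For k = 2, h = 0.5, n = 16 (both arms pooled): 0.5 × 4 / 0.548 = 3.65, so the false-positive rate is 93%.

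Simulation, reading A, 8 per arm, 4,000 runs:

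| h (SD) | False time effect | Time × diet | Day 11 between arms |
|---|---|---|---|
| 0 | 5.3% | 5.3% | 5.4% |
| 0.25 | 41% | 5.5% | 4.9% |
| 0.5 | 93% | 4.8% | 5.4% |
| 0.75 | 99.9% | 5.7% | 4.7% |
| 1.0 | 100% | 4.8% | 4.9% |

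From the formula, for the other cases:

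| Case | h = 0.25 | h = 0.5 |
|---|---|---|
| Pooled, k = 1, n = 16 | 24% | 72% |
| One arm, k = 2, n = 8 | 20% | 60% |
| One arm, k = 1, n = 8 | 13% | 38% |

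These figures show which contrasts are sensitive. They do not estimate the bias in this trial.

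**The case against.** The strongest reply is that the study's questions concern CMC, and the contrasts that answer them are between arms. Both arms collect and handle stool alike, and assignment is random. A handling shift common to both arms cancels from the time-by-diet contrast and is absent from the Day 11 comparison. The simulation agrees: both stay near 5%. This stands, and it limits the point to the time main effect and within-arm fecal changes. Trends across inpatient days and the biopsy comparisons are not affected either.

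A reader might infer more in four places, and the documents do not support it.

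- **That every pre-CMC stool is a home sample, so handling and period coincide exactly.** CMC starts at Day 1 dinner. A stool passed on the unit earlier that day would be pre-CMC and frozen at once.
- **That home material as a whole waits 48 h.** That figure is a ceiling, the visit sections imply less, and one portion is put in ethanol immediately.
- **That a poorly handled baseline weakens a covariate adjustment.** No stool measure is a covariate anywhere in the plan. The only adjusted regression, in Section 7.2.3, uses weight change and BMI.
- **That the CMC effect itself is biased.** That would need handling to act differently in the two arms, and nothing in the documents suggests it.

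**Conclusion.** The point holds in a limited form. By design, 8 to 16 of the 96 stools per arm are handled differently, including the Visit 2 baseline and probably the post-washout reference. The home-versus-inpatient part of the RM-ANOVA time effect, and any within-arm before/after test on a fecal measure that uses a home stool, cannot be separated from handling. The Day 11 between-arm and time-by-diet contrasts remain valid.

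The size of the bias is unknown. The false-positive rates above rest on an assumed correlation of 0.5 and an assumed range of shifts. They show only that a moderate shift would be enough to mislead. This is a minor, easily corrected weakness in the analysis plan and does not threaten the between-arm comparison.

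**What to change.** In Section 7.2.1, and for paired tests on fecal measures in Sections 6.4.3 and 7.2.3:

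1. Base conclusions about CMC on the between-arm and arm-by-time contrasts.
2. Estimate time effects only among like-handled stools. For washout, compare the Visit 2 and pre-admission home stools. For the intervention, use inpatient stools, with a unit stool passed before Day 1 dinner as the pre-CMC reference where one exists.
3. Add a sensitivity analysis restricted to inpatient stools.
4. State whether the Day 1 stool is the home or the unit sample, and which home portion (ethanol or remainder) goes to each assay.

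A model term for handling type is not a good substitute. Where a participant's pre-CMC stools are all home samples, it cannot be separated from the before/after step.

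The cost is plan wording and one extra analysis. The drawback is incompleteness. Section 4.2 admits people with a bowel movement only every two days, so some will have no unit stool before Day 1 dinner, and the within-arm inpatient contrast will rest on fewer than 8 participants per arm.

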6.1.4 Sigmoidoscopy to obtain mucosal biopsy samples

On days 1 and 11, each participant will undergo a sigmoidoscopy to obtain biopsies from the area of approximately 15 cm from the anal verge, which correlates with approximately the rectosigmoid junction. No bowel preparation will be utilized prior to the sigmoidoscopy since it is unknown what affect the bowel preparation may have on the fecal microbiome or the mucosally adherent microbiome. No sedation medications will be administered.

16 biopsies obtained from the distal 20 cm of the colon will be collected; 4 placed in Carnoy solution for non-denaturing confocal microscopy, 4 flash frozen in liquid

nitrogen, 4 placed in RNAlater, and 4 will be kept fresh for immediate cell isolation studies. Additional biopsies may be taken (up to a total of 20), to replace lost/dropped/unusable biopsies (i.e., if the biopsy is too small), for quality control and/or for methods testing.

6.1.5 Rectal Swabs

On Day 1, prior to the flexible sigmoidoscopy, participants will undergo a rectal swab for assessment of the mucosally-associated gut microbiota.

Rectal swabs will be obtained during the physical examination by the CHPS nurse practitioner or study investigator. Four total swabs will be collected per participant. Three (3) sterile swabs will be inserted 3 cm into the rectum, turned 360 degrees, removed, placed into a sterile tube, and frozen at -80 degrees celcius until analysis. One of the swabs will be delivered immediately to [name] laboratory for anaerobic culture. Finally, one (1) swab will be waved in the air and collected as a control.

6.1.6 Food Satiety questionnaire

On days 2, 3, 5, 6, 9, and 10, following lunch, participants will complete a standard food satiety questionnaire. A standardized 150mm VAS approach to measuring satiety and hunger as described by Hill and Blundell and modified by Doucet will be employed.^{81, 82} The following questions will be asked at 12:15h before lunch is served. Participants will be given their meal at 12:30h and will finish eating their meal by 13:00h. They will complete the questionnaire again at 13:00h. The questions should be asked in the participant's room with all lights on and with no food in the room.

Questions to be asked are as follows.

- 1) How strong is your desire to eat (very weak to very strong)?
- 2) How hungry do you feel (not hungry at all to as hungry as I have ever felt)?
- 3) How full do you feel (not full at all to very full)?
- 4) How much food do you think you could eat (nothing at all to a large amount)?
- 5) How preoccupied are you with thoughts of food (no thoughts to very preoccupied)?
- 6) What is your urge to eat (no urge to strong urge)?

6.1.7 Oral glucose tolerance test

On day 1 and 11, participants will complete a 2.5 hour oral glucose tolerance test. This test will be completed prior to breakfast following a 12 hour fast. At 08:00h, a catheter will be placed in an antecubital or forearm vein for blood sampling, with the arm placed in a heating pad to promote arterialization of venous blood. After 20 min of acclimatization to the catheter placement, baseline blood samples will be taken at -5 and -1 min prior to the ingestion of 75 grams anhydrous oral glucose over a 5 min period starting at $t = 0$ at ~08:30h. Subsequent blood samples will be collected at $t = 15, 30, 60, 90,$ and 120 min post-ingestion. All samples will be collected on ice into chilled EDTA tubes with protease inhibitor cocktail containing DPP4-inhibitor added immediately, centrifuged at 4 degrees C, aliquoted in ice, and stored at minus 80 degrees C until biochemical analysis. A total of 4 ml of blood will be collected at each

test. Glucose, free fatty acids, insulin, glucagon, and GLP-1/GIP will be the substances tested.

6.1.8 PROMIS scale

On days 1 and 11, participants will complete the PROMIS scale for abdominal pain and gas/bloating. This should be completed prior to eating study food that day. On Days 1 and 11, this can be completed during the oral glucose tolerance test.

6.2 Sequence of study activities

Visit Number	Visit 1	Visit 1.1	Visit 2	Visit 2.1	Visit 3											Visit 4	Visit 5	Visit 6
	-60 to -9	-7	-4	-3 to -1	1	2	3	4	5	6	7	8	9	10	11	24	48*	107*
Study Day																		
Food pick up			X															
Emulsifier free diet				X														
Randomized diet					X	X	X	X	X	X	X	X	X	X	X			
Satiety Questionnaire						X	X		X	X			X	X				
Record Calories Consumed					X	X	X	X	X	X	X	X	X	X	X			
DHQLI					X													
Fitbit Data Collection			X	X	X	X	X	X	X	X	X	X	X	X	X			
Walks (as needed)					X	X	X	X	X	X	X	X	X	X	X			
Weight	X		X		X	X	X	X	X	X	X	X	X	X	X			
Waist Circumference	X																	
CBC	X																	
CMP	X														X			
PT and INR	X																	
HbA1c	X																	
Fasting Lipid Panel	X																	
Vital Signs	X		X		X	X	X	X	X	X	X	X	X	X	X			
Physical Exam	X				X													
Medical History	X																	
24 hour recall x3		X																
Urine Collection	X		X		X	X	X	X	X	X	X	X	X	X	X			
Stool Collection			X		X	X	X	X	X	X	X	X	X	X	X		X	X
Stool Kit Pick Up	X		X											X		X		
Stool Kit Return			X		X											X	X	
Blood Collection			X		X	X	X					X		X	X	X		
PROMIS scale					X										X			
Oral glucose tolerance test					X										X			
Rectal swabs					X													
Sigmoidoscopy with biopsy					X									X				
Monitoring adverse events					X	X	X	X	X	X	X	X	X	X	X	X		
Concomitant medications	X		X		X	X	X	X	X	X	X	X	X	X	X			
AE Follow Up Phone Call																X		
Follow Up Questionnaire																	X	X

*Fitbit will be distributed at Visit 2 (4 days prior to admission to inpatient CHPS).

*Urine pregnancy test will be conducted for females at screening and Day 1 of inpatient procedures.

6.2.1 Pre-screening and Informed Consent

Each potential participant will be pre-screened for eligibility over the phone. Additionally, inclusion and exclusion criteria may be reviewed with the potential participant during the pre-screening visit. Those who appear to meet all eligibility criteria will then be introduced to the study. Full explanation of the study and the general procedures will be explained thoroughly to the participant. Potential participants will be given an opportunity to ask questions and have them answered by study staff.

Potential participants will sign and date written consent to participate *prior* to screening visits. No steps for screening or beyond will occur prior to informed consent. The consent process will be completed in English.

A copy of the signed consent form will be given to the participant. The original signed consent form should be placed in the participant study file. A second copy should be placed in a confidential study folder containing copies of consents for all study participants. A third copy will be provided to the CHPS.

6.2.2 Screening (Visit 1)

Screening evaluation should be completed no more than 60 days prior to admission to the CHPS. After providing informed consent, the participant's medical history will be collected to assess for exclusion criteria, including vital signs and demographic data. Demographic data collected will include age, sex, race, ethnicity, lifetime weight history, current and recent medication use, and past medical and surgical history. A physical exam will also be conducted.

In addition, blood will be drawn for CBC, comprehensive metabolic panel, lipid panel, Hba1c, coagulation parameters following an overnight fast. Women will complete a urine pregnancy test.

During the screening process, participants will be presented with the study diets to assure that they are able to consume this for a 14 day period. Screening will not proceed further unless participants agree that they can follow the study diet, regardless to which they are assigned.

Demographics

Birth date

Sex

Race and ethnicity

PMH & concurrent medical problems

Current medications and dose

Tobacco use

Alcohol use

Exclusion criteria lab work

CBC

Comprehensive metabolic panel (CMP)

PT and INR

Fasting lipid panel

Urine pregnancy test

Hba1c

Physical exam

